8.1.2 Primary analysis of the primary efficacy endpoint(s)

Summary descriptive statistics for each endpoint and change from baseline for each endpoint, including to follow-up, will be provided by treatment and Nominal Day (D1(Baseline), D2, D6, D15 and Follow-Up).

Each endpoint (PaO₂/F_iO₂ ratio, P(A-a)/O₂ gradient, a/A PO₂ ratio) will be analyzed separately using a Mixed Model Repeated Measures (MMRM) analysis with fixed effects for Baseline, treatment, Nominal Day (using Nominal Days, D6 and D15), Baseline*Nominal Day interaction and treatment*Nominal Day interaction where Nominal Day is categorical. Participant will be fitted as a random effect and an unstructured covariance will be used, unless it fails to converge,

when other covariance structures will be considered. Mean change from baseline to D6 and D15 for each treatment arm and differences between treatments in mean change from baseline to D6 and D15, their 95% confidence intervals and p-values will be estimated directly from the model.

The primary analysis will not adjust for missing data, other than how they are handled in MMRM under the assumption that the data are missing at random. This assumption implies that the behaviour of the post dropout observations can be predicted from the observed endpoints, and therefore the response can be estimated without bias using exclusively the observed data.

The following results from the model will be tabulated:

- LSMEANS (adjusted for baseline levels) and 95% confidence intervals for change from baseline by treatment and Nominal Day for each endpoint (PaO₂/FiO₂ ratio, P(A-a)/O₂ gradient, a/A PO₂ ratio)
- Estimates of the differences between treatments in mean change from baseline, 95% confidence interval and p-value at D6 and D15 for each endpoint (PaO₂/FiO₂ ratio, P(A-a)/O₂ gradient, a/A PO₂ ratio).
- Mean percentage change from baseline will be estimated from the results of the MMRM model for D6 and D15 for each Treatment Arm, together with 95% confidence intervals.

Plots of the results from the MMRM will be provided for LSMEANS (adjusted) of change from baseline and 95% CI by treatment on each Nominal Day of Interest and the mean differences of the LSMEANS between treatments and their 95% CI. Distribution plots for the estimated mean differences (Arm A -Arm B) between treatments will be provided for each nominal day where the x-axis will represent the range of differences between treatments and the area under the curve will present the probability of the mean difference in means being greater than specified values.

8.1.3 Sensitivity analyses of the primary efficacy endpoint(s)

In order to explore the validity of assumptions behind the primary analyses and after review of residual plots, the data for each endpoint (data only come from the set of positive real numbers) (PaO₂/FiO₂ ratio, P(A-a)/O₂ gradient, a/A PO₂ ratio) may be first log transformed and each endpoint will be analysed separately using a MMRM model with fixed effects for Baseline, treatment, Nominal Day (D1,D6, D15), Baseline*Nominal Day interaction and treatment*Nominal Day interaction where Nominal Day is categorical. Participant will be fitted as a random effect and an unstructured covariance will be used, unless it fails to converge, when other covariance structures will be considered.

Mean change from baseline to D6 and D15 for each treatment arm and differences in the means on the log scale between Arm A and Arm B (Arm A- Arm B) for each VISIT (Day 6, 15) will be estimated directly from the models.

The following results from the model will be first back-transformed and then tabulated:

- LS geometric means (adjusted for baseline) and 95% confidence intervals for by treatment and Nominal Day for each endpoint (PaO₂/FiO₂ ratio, P(A-a)/O₂ gradient, a/A PO₂ ratio) to provide geometric LSMEANS(adjusted for baseline) and 95% confidence limits

- Estimates of the treatment differences on the log scale between treatments and 95% confidence interval at D6 and D15 for each endpoint (PaO₂/FiO₂ ratio, P(A-a)/O₂ gradient, a/A PO₂ ratio) to provide the ratio of geometric means and 95% confidence limits. The p-values for these differences will also be provided in the table.

These analyses will be repeated using the alternate baseline (section 3.2.2.2) to include participants with a baseline soon after dosing.

An additional sensitivity analysis will repeat both the primary analysis and sensitivity analysis above using LOCF for participants with missing data on either D6 or D15 that was not due to discharge:

- due to death prior to D15, which could mean both D6 and D15 are missing or just D15. The impact of both being missing will be explored using residuals, as the LOCF method will necessarily mean that the change from baseline for these participants is nominally 0, as the baseline value will be carried forward

To explore the impact of age, sex, weight and ethnicity on the results, the analyses described above and in section 8.1.2 will be repeated including sex, age (in years), BMI and weight and ethnicity as additional covariates.

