11.2. Type of statistical methods

All primary and secondary endpoints will be summarized and where relevant represented graphically

Primary endpoint:

The change from baseline in PaO₂/FiO₂ ratio will be analyzed using a Mixed Model Repeated Measures (MMRM) analysis with a fixed effect for Baseline PaO₂/FiO₂ ratio, treatment, day and treatment by day interaction, where day is categorical. Subject will be fitted as a random effect and an unstructured covariance will be used unless it fails to converge, where other covariance structures will be considered. Other covariates, such as gender, may also be included in the model, if by the time of the analysis these have been identified as key differentiators in terms of COVID-19 recovery. If the variability is shown to be inappropriate for this additive model, then a log transformation of the PaO₂/FiO₂ ratio may be considered.

Data from SOC in another study with a very similar protocol may be incorporated into the analysis using a Bayesian frame work. This will be described more fully in the statistical analysis plan (SAP).

A similar analysis for the P(A-a)O₂ gradient will be completed

Other Endpoints:

Other continuous endpoints will be analyzed in a similar way using an MMRM.

Response rates, such as 28 day all-cause mortality a logistic regression will be used.

Count data will use a generalized linear model with a log link unless the model is either over or under dispersed and then an alternative approach will be used. If it is counts out of a fixed number of days, then a logistic regression will be considered.

For the final follow up, a survival analysis with Kaplan-Meir plots will be created covering from Day 1 to end of follow up.

The detail around the analyses will be explained in more detail in the SAP and as this is an exploratory study, additional analyses may be considered to explore the data more fully.

Interim analyses: will be performed when 42 patients have reached primary endpoint analysis.

After half the patients have completed day 15 an interim analysis will be completed to understand if there is already enough evidence to prompt further work on COVID-19 treatment with Zilucoplan®. There is no plan to stop the study at this stage.

Analyses will also be completed when all patients have finished day 28 to assess all pre-follow up assessments and 28 day mortality (via phone call). This will enable key results to be understood as soon as possible without compromising the study.

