8.1.1 Derivations of primary efficacy endpoint(s)

Measurements to derive PaO₂/FiO₂ ratio (measure of severity of hypoxemia), P(A-a) O₂ gradient (always positive and a reflection of the difficulty oxygen has at crossing the alveolar capillary membrane and increases with age and FiO₂ related to determine if it is normal.) and a/A PO₂ ratio are to be taken at Baseline, and at least at pre-dose (for arm A) on Day 6 and Day 15 (or at discharge, whichever comes first). Measurements for Arm B can be taken at any time, but preferably at the same time on each Day for every participant to allow for diurnal variation, at least on Days 1, 6, 15 (or at discharge, whichever comes first). Where possible, more frequent measurements will be taken in both arms, preferably daily.

eCRFs indicate that FiO₂ will be taken daily, however PaO₂ and PaCO₂ only at Screening/Day-1, nominal D1, nominal D6 and nominal D15.

Therefore, the derived parameters should be calculated using the data from the arterial blood gas (ABG) eCRF and not from Vital Signs.

Calculation

PaO₂ is the partial pressure of oxygen in the **arterial blood** and provided on the CRF. The Alveolar Gas Equation provides an estimate of PAO₂.

$$\text{PAO}_2 = (\text{P}_{\text{atm}} - \text{P}_{\text{H}_2\text{O}}) \text{FiO}_2 - \text{PaCO}_2 / \text{RQ}$$

(=partial pressure of oxygen in the **alveoli**)

Where:

P_{atm} is atmospheric pressure at sea level = constant 760 mm Hg

P_{H₂O} is partial pressure of water in alveoli = constant 45 mm Hg

F_iO₂ is fractional concentration of O₂ in inspired air, from eCRF (or 21% (0.21) if participant is not on supplemental oxygen

PaCO₂ is partial pressure of carbon dioxide in alveoli from eCRF

RQ = respiratory quotient = constant 0.82 (for typical human diet)

$$\text{P(A-a) O}_2 \text{ gradient} = \text{A-a gradient} = \text{PAO}_2 - \text{PaO}_2$$

$$\text{a/A PO}_2 \text{ ratio} = \text{PaO}_2 / \text{PAO}_2$$

Given that ABG is only measured on specified days, change from baseline to each of these days will be calculated for each of these endpoints for each participant [For example, (D6 - Baseline), (D15 - Baseline)].

Note:

All the above calculations should be carried out and used to verify the result for variables that are directly collected on the eCRF. Any discrepancy should be listed but the ones on the eCRF should be primarily used.

Increasing values for PaO₂/F_iO₂ ratio indicates improvement over time (normal considered ~470 mmHg)

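### SAP 8.1.3 allows a log analysis of the A-a gradient on the ground that it is always positive, but the SAP's own formula can give zero or negative values

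*SAP*

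**What the plan says.** SAP 8.1.1 describes the P(A-a)O2 gradient as "always positive and a reflection of the difficulty oxygen has at crossing the alveolar capillary membrane". The same section computes alveolar pressure from fixed constants and defines the gradient as alveolar minus arterial pressure. It adds that these calculations are used to verify values collected directly on the eCRF, and that the eCRF values take priority.

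SAP 8.1.2 makes the primary analysis an MMRM of untransformed change from baseline, run separately for PaO2/FiO2, the gradient and the a/A ratio.

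SAP 8.1.3 then says that, after review of residual plots, "the data for each endpoint (data only come from the set of positive real numbers") "may be first log transformed and each endpoint will be analysed separately using a MMRM model". Results are back-transformed to geometric means, ratios of geometric means, confidence intervals and p-values. The analyses are repeated with the alternate baseline, with LOCF for some missing values, and with extra covariates.

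Protocol 11.2 has a conditional log option for PaO2/FiO2: "If the variability is shown to be inappropriate for this additive model, then a log transformation of the" ratio may be considered. It later says that the gradient will be analysed in a similar way.

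**The concern.** The SAP's justification for taking logs is that the data are positive. For PaO2/FiO2 and a/A that holds for any realistic input. For the gradient it does not follow from the definition, because a difference of two pressures can be zero or negative.

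The conditions for this exist in the trial. Unless ventilated, participants have the D6 and D15 or discharge blood gas taken after at least three minutes off oxygen, so recovered participants supply near-normal room-air values. SAP 3.2.1.3 also carries a discharge value forward: one obtained by Day 6 stands for both D6 and D15, so one non-positive value could be unusable at both primary time points.

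The SAP gives no offset, floor, exclusion or listing rule for such values. Software would ordinarily return a missing result. Because a lower gradient is better, the loss would depend on the value itself, which does not fit the missing-at-random assumption in SAP 8.1.2. Small positive values are a second problem: 0.2 against 19 mmHg is a 95-fold ratio, so a few recovered participants could dominate a log-scale result.

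**Working it through.** **Inputs from SAP 8.1.1.** Atmospheric pressure "is atmospheric pressure at sea level = constant 760 mm Hg"; water vapour pressure "is partial pressure of water in alveoli = constant 45 mm Hg"; RQ 0.82; FiO2 0.21 off oxygen; PaO2/FiO2 "normal considered ~470 mmHg"; normal gradient Age/4 + 4.

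**Assumed.** PaCO2 is not given in the documents; 35 to 45 mmHg is used for the range below.

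**Formula.** Gradient = (760 - 45) x FiO2 - PaCO2/0.82 - PaO2. On room air this is 150.15 - PaCO2/0.82 - PaO2.

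**At the SAP's normal PaO2/FiO2.** PaO2 = 470 x 0.21 = 98.7 mmHg.
- PaCO2 35: 150.15 - 42.68 - 98.7 = +8.8
- PaCO2 40: 150.15 - 48.78 - 98.7 = +2.7
- PaCO2 45: 150.15 - 54.88 - 98.7 = -3.4
- Zero at PaCO2 = (150.15 - 98.7) x 0.82 = 42.2

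**PaO2/FiO2 at which the room-air gradient reaches zero.** 512, 483 and 454 at PaCO2 35, 40 and 45. The SAP's normal of 470 lies inside this range.

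**Where the problem does not arise.** At PaO2/FiO2 350 on room air (the inclusion limit) and PaCO2 40, the gradient is 150.15 - 48.78 - 73.5 = +27.9, and it reaches zero only at PaCO2 62.9. At FiO2 0.40 and PaCO2 40 the zero point is PaO2/FiO2 593. Baseline values and values on oxygen are therefore largely safe; the issue is confined to recovered, room-air values.

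**The SAP's normal gradient.** Age/4 + 4 gives 8.5 at age 18, 19 at 60 and 24 at 80. At PaCO2 40 these correspond to PaO2/FiO2 of 442, 392 and 368, all below the zero point of 483. By this standard a typical recovered adult has a positive gradient.

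**Illustrative share at or below zero.** Room air, PaO2 and PaCO2 normally distributed, PaCO2 mean 36 to 40 with SD 4. None of these distributions is in the documents.

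| PaO2 mean (SD) | Independent | Correlation -0.5 |
|---|---|---|
| 80 (10) | 0.9-2.7% | 0.1-0.7% |
| 85 (12) | 5-10% | 2.1-5.9% |
| 90 (12) | 10-19% | 6-14% |

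Under independence a further 0.5% to 4.5% lie between 0 and 2 mmHg. A mean PaO2 of 90 on room air is PaO2/FiO2 429, above the 400 implied by the sample-size figures (320 + 80), so the last row is optimistic.

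**Effect on the between-arm ratio (independent PaO2 and PaCO2).** The geometric-mean ratio among retained positive values is set against the ratio of medians of all values.
- Mean PaO2 85 against 80, SD 10, PaCO2 36 to 40: 0.79 to 0.77 retained, 0.81 to 0.77 for medians. No attenuation.
- Mean PaO2 90 against 80, SD 12, PaCO2 40: 0.62 retained, 0.53 for medians. Attenuation.

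Dropping non-positive values pulls the ratio towards 1; retained near-zero values pull it away. Which dominates depends on the data.

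**The case against.** The strongest reply is that little rests on this. The log step is optional, follows residual review and is a sensitivity analysis; the primary MMRM keeps every non-positive gradient. SAP 4.5 says there is effectively one primary endpoint, PaO2/FiO2, whose logarithm is unaffected. The SAP's normal gradient is clearly positive at every adult age. eCRF values take priority over the formula, and the documents do not show how any eCRF gradient is obtained. A non-positive value may also reflect a high PaCO2 or an FiO2 error, so it is not always a best outcome. All of this stands and limits the point to a minor one. It does not make the positivity statements true: nothing described for the eCRF keeps its values above zero, and no rule covers those that are not.

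Three stronger readings are tempting and are not supported.
- That the SAP goes beyond the protocol in logging the gradient. Protocol 11.2 names PaO2/FiO2 in the log sentence, but then plans a similar analysis for the gradient, which can reasonably carry the option over.
- That the log analysis is always biased against an effective treatment. The scenarios above show attenuation in one case and none in the other.
- That this would probably be the reported result. SAP 8.1 does present whichever analysis is most appropriate, but undefined logarithms would count against choosing this one.

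**Conclusion.** The point holds as a wording defect with a limited consequence. Both positivity statements are wrong for the gradient as the SAP defines it: at PaO2/FiO2 470 on room air it is zero or negative from PaCO2 42.2 upward. If the log model is run for the gradient, some well-oxygenated values can be lost for a reason tied to the outcome, others can become extreme, and the ratio of geometric means can be distorted in either direction.

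The share affected is about 0.1% to 19% under the assumed PaO2 and PaCO2 distributions and correlations; the documents do not fix it. The formula arithmetic needs only the SAP's constants and a stated PaCO2. The untransformed primary MMRM and the log analyses of PaO2/FiO2 and a/A are unaffected.

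**What to change.** In SAP 8.1.3, restrict the log-scale MMRM, and its alternate-baseline, LOCF and covariate repeats, to PaO2/FiO2 and a/A. Delete the statements in 8.1.1 and 8.1.3 that the gradient is always positive. State that zero and negative gradients are valid values and stay in the untransformed analysis. If the gradient residuals are skewed, a rank-based or bootstrap check could be added; this is optional.

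The cost is SAP wording only: no new data, no change to the primary analysis and no effect on sample size.

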3.2.2 Definition of Baseline values

3.2.2.1 General baseline

In general, Baseline values for efficacy and safety endpoints will be determined from the last non-missing data value collected prior to the first dose of Zilucoplan®, unless otherwise noted for a specific type of data in Arm A. For Arm B, baseline values will be the first value taken on the designated Day 1 of study medication, defined as the day the participant first receives IV antibiotic. For endpoints which measurements are not taken on Day 1, Baseline will be the value taken at Screening.

Note that for the Nominal Day variable, identified baseline values (whether they were actually taken at Day -1/Screening or pre-dose D1) will be mapped to D1. If this value was taken at Day -

1 (Screening), there will be a missing value associated with the Day -1 (Screening) level in order not to duplicate results.

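### The optional log-scale sensitivity MMRM in SAP 8.1.3 lists Day 1 as a response day although Day 1 is also the baseline covariate, so on the natural reading its planned unstructured covariance is singular

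*SAP*

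**What the plan says.** SAP 8.1.3 makes the log-scale analysis optional: once residual plots have been reviewed, the values of each primary endpoint "may be first log transformed and each endpoint will be analysed separately". The terms of that model are then set out as follows: "using a MMRM model with fixed effects for Baseline, treatment, Nominal Day (D1,D6, D15), Baseline*Nominal Day interaction". A treatment by Nominal Day term completes the list. For the covariance, "an unstructured covariance will be used, unless it fails to converge, when other covariance structures will be considered". Results are back-transformed and tabulated, and "The p-values for these differences will also be provided in the table". The section then repeats the analysis with the alternate baseline, with LOCF for data missing for reasons other than discharge, and with added demographic covariates.

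SAP 3.2.2.1 settles what the D1 value is: "identified baseline values (whether they were actually taken at Day -1/Screening or pre-dose D1) will be mapped to D1".

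Elsewhere the SAP treats only D6 and D15 as outcome days:

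- The primary model in SAP 8.1.2 has "Nominal Day (using Nominal Days, D6 and D15" as the levels of Nominal Day.
- SAP 8.1.1 defines change from baseline for those days: "For example, (D6 - Baseline), (D15 - Baseline".
- SAP 8.1.3 itself wants treatment differences "for each VISIT (Day 6, 15) will be estimated directly from the models".

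SAP 8.1.3 does not state whether Baseline is also logged. It also leaves open whether the modelled response is the log value or the change in log value.

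**The concern.** A baseline measurement can enter a repeated-measures model as a covariate or as one of the responses. This model uses it as both, and it crosses Baseline with day, so D1 has its own baseline slope. On a common log scale the D1 response is then reproduced exactly by its own predictor and no residual variation is left at D1. An unstructured covariance needs a positive variance on every day, so the planned structure has no valid estimate.

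Two things are at stake. First, the analysis would be driven to its fallback by its own specification rather than by a numerical accident, and the fallback is unnamed. Second, some fallbacks would run without complaint and give wrong standard errors: a structure with one variance for all days would average in the zero at D1. The confidence limits and p-values from this model are to be tabulated, and the same model feeds three sets of repeats.

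**Working it through.** **Inputs.** From SAP 2.4: 81 participants, 54 and 27 by arm; SD 105; a target difference of 80, being 25% of 320; two-sided 5%; dropout below 10%. From SAP 8.1.3: the model terms and the covariance rule. From SAP 3.2.2.1: D1 equals baseline. The correlations and variance ratios below are assumptions, because the documents give none.

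**The plan's own figure.** The SE of the difference is 105 × √(1/54 + 1/27) = 24.75. Then 80/24.75 − 1.96 = 1.27, and power is Φ(1.27) = 89.8% (89.1% with the t distribution). With 10% dropout it is 86.6% (85.7%). The stated power above 85% is reproduced and is not in question.

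**Step 1: the D1 residual.** Let b be the baseline value. All terms are crossed with day, so each day has its own intercept, baseline slope and treatment effect.

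- *Log response, log Baseline.* The D1 response is log b and the covariate is log b. Intercept 0, slope 1 and treatment effect 0 fit exactly, so all D1 residuals are zero.
- *Change in log value as response.* The D1 response is log b − log b = 0 for everyone. All D1 residuals are zero on either scale of Baseline.
- *Log response, unlogged Baseline.* The D1 residual is the curvature of log b against b, which is small but not zero.

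**Step 2: numerical confirmation.** One data set was simulated with 54:27 allocation, log SD 105/320 = 0.33, and assumed correlations of 0.5 (D1–D6), 0.4 (D1–D15) and 0.6 (D6–D15).

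| Response / Baseline | D1 residual variance | D6 | D15 | Unstructured matrix over D1, D6, D15 |
|---|---|---|---|---|
| log / log | 0 | 0.059 | 0.071 | singular (eigenvalues 0, 0.035, 0.094) |
| change in log / log | 0 | 0.059 | 0.071 | singular |
| change in log / unlogged | 0 | 0.059 | 0.072 | singular |
| log / unlogged | 0.0043 | 0.060 | 0.073 | can be fitted |

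In the log/log case the REML criterion contains (81 − 3) × ln(D1 variance) and nothing that offsets it. It therefore falls by 78 × ln 10 = 179.6 for each tenfold drop in the D1 variance. Between 10⁻¹ and 10⁻¹⁴ it goes from −468 to −2803, with no finite minimum. With D6 and D15 only, the matrix is positive definite (eigenvalues 0.035 and 0.094). The singularity is algebraic and does not depend on the assumed SD or correlations.

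**Step 3: what a one-variance fallback would do.** Assume compound symmetry over the three days, complete data, and residual variances 0, v6 and v15. The pooled variance is (0 + v6 + v15)/3, and the type I error on a given day is 2 × [1 − Φ(1.96 × √(pooled/v))], where v is that day's variance. With v6 = v15 = v:

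- pooled variance = 2v/3;
- SE ratio = √(2/3) = 0.816, so standard errors are 18% too small;
- type I error = 2 × [1 − Φ(1.600)] = 10.95%, and 95% interval coverage is 89.0%.

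| v15/v6 (assumed) | D1 kept: D6 / D15 | D1 left out: D6 / D15 |
|---|---|---|
| 1 | 10.95% / 10.95% | 5.0% / 5.0% |
| 2 | 5.0% / 16.6% | 1.6% / 9.0% |

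The second row shows that part of the distortion under unequal variances comes from forcing a common variance, whether or not D1 is present.

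Simulation agrees. With 20,000 null trials, equal variances and assumed correlations of 0.5, type I error was 10.5% at D6 and 10.8% at D15 with D1, against 5.0% and 5.2% without. Under the Step 2 correlations the D15 figures were 11.5% with D1, 5.5% without, and 4.9% when D15 had its own variance.

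**Step 4: point estimates.** With complete data and every term crossed with day, the D6 and D15 coefficients are the same whether or not D1 is in the model.

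**The case against.** The strongest reply is that this is a drafting slip which the surrounding text already contradicts. SAP 8.1.3 asks for estimates at D6 and D15 only, and SAP 8.1.1 and 8.1.2 agree. The table shells, which are a separate document, may settle the days. That shows the intent, but it does not make the stated model fittable. Nor can D1 be rescued as a deliberate choice: a model that keeps the baseline visit as a response would not also carry Baseline and Baseline by day as covariates.

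Several limits on the consequences do stand. The log analysis is optional. The SAP names no one-variance fallback, so the 11% figure is conditional on an assumed choice. A fallback with separate variances by day would not understate the standard errors. If Baseline were left unlogged and the response were the log value, the unstructured model could be fitted, although that reading is strained when the endpoint data are to be logged before modelling.

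Three stronger readings are tempting but not supported:

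- *The trial's primary test has inflated error.* It does not. The SAP 8.1.2 model uses D6 and D15 only.
- *The replacement structure must be chosen after the data are seen.* A singular fit would show on dummy data, and SAP section 1 provides for an amendment if key methodology has to change before database lock.
- *The raw scale must be fixed as the primary result, or a separate-ANCOVA fallback added.* Which scale is presented is a separate matter, and Protocol 11.2 expressly leaves the log scale open. Separate ANCOVAs would give up the joint missing-at-random handling in SAP 8.1.2 to cover a failure that did not occur: a two-visit unstructured model converged in 6,000 of 6,000 simulated trials with 10% of D6 and 15% of D15 values missing (assumed).

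**Conclusion.** The model in SAP 8.1.3 is wrong as written. With Baseline on the log scale alongside the response, or with change as the response, the D1 residuals are identically zero and the specified unstructured covariance cannot be estimated. This rests only on the model terms and on the mapping of baseline to D1.

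The inferential consequence is conditional. It requires that the optional analysis is run, that D1 is kept, and that the structure adopted has one variance for all days. With equal D6 and D15 variances, standard errors are then 18% too small and type I error is about 11% rather than 5%. With a twofold variance difference, type I error ranges from 5.0% to 16.6% by day.

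The primary analysis and the sample size are not affected, and neither are the complete-data point estimates. Severity is minor, though the alternate-baseline, LOCF and covariate-adjusted repeats inherit the same specification.

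**What to change.** In SAP 8.1.3, change the Nominal Day levels from D1, D6 and D15 to D6 and D15, matching SAP 8.1.2 and the estimates that 8.1.3 itself requests. In the same sentence, state that Baseline is log-transformed whenever the response is. The repeats in 8.1.3 then inherit the corrected model without further edits.

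The cost is one edited sentence. Data collection, sample size and the primary analysis do not change, and no information about D6 or D15 is lost, because D1 still enters as the covariate.
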